#### 4.1 Randomization

Please note that no blinded starter supplies will be available for this study. Blinded, patient-specific clinical supplies will be shipped from the Pharmaceutical Management Branch (PMB) of the NCI to the registering investigator at the time of patient randomization and should arrive within five working days (see Section [8.0](#)).

For sites within the United States, the Pharmaceutical Management Branch will ship patient-specific open label exemestane with the initial blinded, patient specific supplies of entinostat or placebo.

**Please note that when a patient has been successfully randomized, the confirmation of randomization will indicate that the patient is on arm X. The patient will actually be randomized to arm A or B, but as this is a double-blind trial, that information cannot be displayed.**

At time of randomization, the following information will be requested:

- 4.1.1 Protocol Number
- 4.1.2 Investigator Identification
  - Institution and affiliate name
  - Investigator's name
- 4.1.3 Patient Identification
  - Patient's initials (first and last)
  - Patient's Hospital ID and/or Social Security number
  - Patient demographics
    - Gender
    - Birth date (mm/yyyy)
    - Race

- Ethnicity
- Nine-digit ZIP code
- Method of payment
- Country of residence

#### 4.2 Eligibility Verification

Patients must meet all of the eligibility requirements listed in Section [3](#).

#### 4.3 Stratification Factors

- Setting in which patient developed resistance to prior non steroidal AI treatment (adjuvant vs. metastatic)
- Geographic region (USA vs. other)
- Visceral disease (yes vs. no)

**NOTE:** Visceral disease for this protocol refers to liver and/or lung involvement.

Rev. 10/15

- Prior fulvestrant use (yes vs. no)

Rev. 10/16

#### 4.4 Additional Requirements

4.4.1 Patients must provide a signed and dated, written informed consent form.

**NOTE:** Copies of the consent are not collected by the ECOG-ACRIN Operations Office – Boston.

Rev. Add5

4.4.2 Clinical data collection for this study will be done through the Medidata Rave clinical data management system. Access to the trial in Rave is granted through the iMedidata application to all persons with the appropriate roles assigned in Regulatory Support System (RSS). To access Rave via iMedidata, the site user must have an active CTEP-IAM account (check at <https://ctepcore.nci.nih.gov/iam>) and the appropriate Rave role (Rave CRA, Read-Only, CRA (Lab Admin, SLA or Site Investigator) on either the LPO or participating organization roster at the enrolling site. To hold Rave CRA role or CRA Lab Admin role, the user must hold a minimum of an AP registration type. To hold the Rave Site Investigator role, the individual must be registered as an NPIVR or IVR. Associates can hold read-only roles in Rave.

Upon initial site registration approval for the study in RSS, all persons with Rave roles assigned on the appropriate roster will be sent a study invitation e-mail from iMedidata. To accept the invitation, site users must log into the Select Login (<https://login.imedidata.com/selectlogin>) using their CTEP-IAM user name and password, and click on the “accept” link in the upper right-corner of the iMedidata page. Please note, site users will not be able to access the study in Rave until all required Medidata and study specific trainings are completed. Trainings will be in the form of electronic learnings (eLearnings), and can be accessed by clicking on the link in the upper right pane of the iMedidata screen.

Users that have not previously activated their iMedidata/Rave account at the time of initial site registration approval for the study in RSS will also receive a separate invitation from iMedidata to activate their account. Account activation instructions are located on the CTSU website, Rave tab under the Rave resource materials (Medidata Account Activation and Study Invitation Acceptance). Additional information on iMedidata/Rave is available on the CTSU members' website under the Rave tab at [www.ctsu.org/RAVE/](http://www.ctsu.org/RAVE/) or by contacting the CTSU Help Desk at [name] or by e-mail at [[contact]](mailto:[contact]).

ECOG-ACRIN has contracted with Alpha Oncology, a contract research organization (CRO) to conduct on-site and remote monitoring activities. The goal of these monitoring activities is to provide source document verification (SDV). Alpha Oncology will be in contact with sites as patients reach the pre-defined milestones for initiation of monitoring activities.

Alpha Oncology will also be conducting data sweeps. The goal of these data sweeps is to assist institutions with timely data entry and query resolution. Alpha Oncology will utilize phone requests and email notifications to request entry of outstanding data and/or completion of open queries. The objective of these sweeps is to collect data; they are not designed as an audit, nor are they intended to generate corrections to previously submitted data.

- 4.4.3 Pathological materials are to be submitted for future undefined research as indicated in Section [11](#).
- 4.4.4 Blood samples are to be submitted for laboratory research studies and future undefined research as outlined in Section [11](#).
- 4.4.5 Plasma samples are to be submitted for population pharmacokinetic studies as outlined in Section [11](#) per patient consent.

**NOTE:** To obtain starter kits and the Site Laboratory Instruction Manual please Email or Fax Appendix IX E2112 Covance Site Information/Initial Kit Order Form to Syndax. Please note Covance requires ten (10) days to process the form and ship the initial kits.

#### 4.5 Additional Registration Training Requirement

##### **Mandatory Participating Site Training Course**

ECOG-ACRIN has developed a training course to provide an overview of the E2112 trial to site research staff and investigators. This training includes information regarding the general protocol overview, data collection and data management, and the imaging component of the trial which will require submission of scans for routine tumor assessments. ECOG-ACRIN recommends all research staff (CRAs, Data Managers, Imaging Staff, Investigators, Pharmacy Staff, etc) involved in E2112 complete the training.

Prior to the first patient enrollment at a participating site, one person from the research staff (i.e. a research coordinator or an investigator) must review and

Rev. 10/16

complete the training course. The course is available 24/7 via the following URL:  
<http://coccg.mindflash.com/PublicCoursePage.aspx?c=832897692>

Rev.4/15

Upon completion of training, please complete the form titled E2112 Mandatory Participating Site Training Form, available in Appendix VII, and submit directly to the CTSU Regulatory Office via [contact] or email: [[contact]](mailto:[contact]). Patient enrollments will be blocked via the OPEN system until one individual at your site completes the required protocol training.

#### 4.6 Instructions for Patients who Do Not Start Assigned Protocol Treatment

If a patient does not receive any assigned protocol treatment, baseline and follow-up data will still be collected and must be submitted through Medidata Rave according to the schedule in the E2112 Forms Completion Guidelines.

Rev. Add5

#### 4.7 Emergency Unblinding

The information provided below is for the use by a physician, nurse, CRA or pharmacist treating the patient. These contact numbers should not be used by patients. Patients should be instructed to call their doctor's office in the event of an emergency or adverse event that may result in the need to unblind the patient.

In the event of an emergency or severe adverse reaction necessitating identification of the medication for the welfare of the patient, please contact the Study Chair, [name], at [contact], or email: [[contact]](mailto:[contact]) first to ensure the reason for unblinding is valid. Then call a member of the ECOG-ACRIN Operations Office – Boston drug team at [contact], Monday through Friday between 9:00 AM and 5:00 PM Eastern Time. For unblinding outside of these hours, contact AnswerConnect at [name]. This service will request the reason for unblinding and then page the on-call ECOG-ACRIN staff who will return your call and provide the unblinded treatment assignment if applicable. Remember, AnswerConnect should only be contacted outside of normal business hours and only in the event of an emergency. The ECOG-ACRIN Operations Office – Boston or AnswerConnect will require the protocol number (i.e., "E2112"), the patient ID number (e.g., "44444"), and the patient initials (e.g., "FL") to unblind the patient. Note that if a patient is unblinded, he/she must discontinue protocol treatment.

NCI CTEP should also be notified of a request for unblinding.

## 5. Treatment Plan

### 5.1 Administration Schedule

Cycle = 4 weeks (28 days)

Rev.4/15

A complete cycle of treatment is defined as 28 days ( $\pm$  3 days) of once daily continuous treatment of exemestane in combination with entinostat/placebo. A new cycle start is defined as the first planned date of entinostat/placebo for the cycle.

Rev. 10/16

Entinostat/placebo should be taken on an empty stomach, at least 1 hour before and 2 hours after a meal/snack. Missed doses should not be made up later.

#### 5.1.1 Arm X (Arms A and B)

Exemestane 25mg po (single dose), days 1-28

Entinostat/placebo 5mg po (single dose), days 1, 8, 15, and 22

Rev. 10/15

Goserelin (Pre/perimenopausal female and all male participants only):  
3.6 mg SubQ injection day 1

Repeat cycles every 28 days until development of disease progression per Section [6](#) or unacceptable toxicity.

**NOTE:** The patient will be randomized to Arm A (Entinostat) or Arm B (placebo), but as this is a double-blind trial, all patients will be identified as on Arm X.

Rev. 10/16

The schedule should be followed as closely as is realistically possible; however, the schedule may be modified due to problems such as scheduling delays or conflicts (e.g., clinic closure, poor weather conditions, vacations, etc.) with the guidance of the protocol chair/designee, as appropriate, and will not be reportable as a deviation unless the endpoints of the study are affected.

Rev. Add5

### 5.2 Adverse Event Reporting Requirements

**NOTE:** **Effective April 1, 2018 expedited adverse event reporting done via CTEP-AERS will use CTCAE version 5.0 terminology and grading. Routine adverse event reporting and dose modifications guidelines on this study will continue to be based on CTCAE version 4.0 terminology and grading.**

#### 5.2.1 Purpose

Adverse event (AE) data collection and reporting, which are required as part of every clinical trial, are done to ensure the safety of the patients enrolled, as well as those who will enroll in future studies using similar agents.

- **Routine reporting:** Adverse events are reported in a routine manner at scheduled times during a trial using Medidata Rave.
- **Expedited reporting:** In addition to routine reporting, certain adverse events must be reported in an expedited manner via CTEP-AERS for timelier monitoring of patient safety and care. The

following sections provide information and instructions regarding expedited adverse event reporting.

5.2.2 Terminology

- **Adverse Event (AE):** Any untoward medical occurrence associated with the use of a drug in humans, whether or not considered drug related. Therefore, an AE can be **ANY** unfavorable and unintended sign (including an abnormal laboratory finding), symptom, or disease temporally associated with the use of a medicinal product, whether or not considered related to the medicinal product.
- **Attribution:** An assessment of the relationship between the adverse event and the protocol treatment, using the following categories.

ATTRIBUTION	DESCRIPTION
Unrelated	The AE is clearly NOT related to treatment.
Unlikely	The AE is doubtfully related to treatment.
Possible	The AE may be related to treatment.
Probable	The AE is likely related to treatment.
Definite	The AE is clearly related to treatment.

- **CAEPR (Comprehensive Adverse Events and Potential Risks List):** An NCI generated list of reported and/or potential AEs associated with an agent currently under an NCI IND. Information contained in the CAEPR is compiled from the Investigator's Brochure, the Package Insert, as well as company safety reports.
- **CTCAE:** The NCI Common Terminology Criteria for Adverse Events provides a descriptive terminology that is to be utilized for AE reporting. A grade (severity) is provided for each AE term.
- **Hospitalization (or prolongation of hospitalization):** For AE reporting purposes, a hospitalization is defined as an inpatient hospital stay equal to or greater than 24 hours.
- **Life Threatening Adverse Event:** Any AE that places the subject at immediate risk of death from the AE as it occurred.
- **Serious Adverse Event (SAE):** Any adverse event occurring at any dose that results in **ANY** of the following outcomes:
  - Death
  - A life-threatening adverse event
  - Inpatient hospitalization or prolongation of existing hospitalization (for  $\geq 24$  hours).
  - A persistent or significant incapacity or substantial disruption of the ability to conduct normal life functions.
  - A congenital anomaly/birth defect.
  - Important Medical Events (IME) that may not result in death, be life threatening, or require hospitalization may be considered serious when, based upon medical judgment, they

may jeopardize the patient or subject and may require medical or surgical intervention to prevent one of the outcomes listed in this definition.

Rev. 10/15

- **SPEER (Specific Protocol Exceptions to Expedited Reporting):** A subset of AEs within the CAEPR that contains list of events that are protocol specific exceptions to expedited reporting. If an AE meets the reporting requirements of the protocol, and it is listed on the SPEER, it should **ONLY be reported via CTEP-AERS if the grade being reported exceeds the grade listed in the parentheses next to the event.**

Rev. Add5

### 5.2.3 Reporting Procedure

This study requires that expedited adverse event reporting use the CTEP Adverse Event Reporting System (CTEP-AERS). CTEP's guidelines for CTEP-AERS can be found at <http://ctep.cancer.gov>. A CTEP-AERS report must be submitted electronically to ECOG-ACRIN and the appropriate regulatory agencies via the CTEP-AERS Web-based application located at <http://ctep.cancer.gov>.

In the rare event when Internet connectivity is disrupted a 24-hour notification is to be made by telephone to

- the AE Team at ECOG-ACRIN [contact])
- the NCI [contact])

An electronic report MUST be submitted immediately upon re-establishment of internet connection.

Rev. Add7

**Supporting and follow up data:** Any supporting or follow up documentation must be uploaded to the Supplemental Data Folder in Medidata Rave within 48-72 hours. In addition, supporting or follow up documentation must be faxed to the NCI [contact]) in the same timeframe.

**NCI Technical Help Desk:** For any technical questions or system problems regarding the use of the CTEP-AERS application, please contact the NCI Technical Help Desk at [[contact]](mailto:[contact]) or by phone at [name].

### 5.2.4 Determination of Reporting Requirements

Many factors determine the reporting requirements of each individual protocol, and which events are reportable in an expeditious manner, including:

- the phase (0, 1, 2, or 3) of the trial
- whether the patient has received an investigational or commercial agent or both
- the seriousness of the event
- the Common Terminology Criteria for Adverse Events (CTCAE) grade
- whether or not hospitalization or prolongation of hospitalization was associated with the event

[figure not shown]
- when the adverse event occurred (within 30 days of the last administration of investigational agent vs.  $\geq$  30 days after the last administration of investigational agent)
- the relationship to the study treatment (attribution)

Using these factors, the instructions and tables in the following sections have been customized for protocol E2112 and outline the specific expedited adverse event reporting requirements for study E2112.

5.2.5 Steps to determine if an adverse event is to be reported in an expedited manner – Arm X (Arms A and B)

Rev. Add5

5.2.5.1 Guidelines for adverse events **OCcurring WHILE ON PROTOCOL TREATMENT AND WITHIN 30 DAYS** of the last administration of the investigational agent(s).

5.2.5.2 Guidelines for adverse events **OCCURRING GREATER THAN 30 DAYS** after the last administration of the investigational agent(s).

If the adverse event meets the definition of a **Serious Adverse Event (SAE)** as outlined by the six criteria in the top portion of the table below in Section 5.2.6, AND has an attribution of possible, probably or definite, the following events require reporting as follows:

**Expedited 24-hour notification followed by complete report within 5 calendar days for:**

- All Grade 4 and Grade 5 AEs

**NOTE:** Any death occurring greater than 30 days after the last dose of investigational agent with an attribution of possible, probable or definite must be reported via CTEP-AERS even if the patient is off study.

**Expedited 10 calendar day reports for:**

- Grade 2 adverse events resulting in hospitalization or prolongation of hospitalization
- Grade 3 adverse events

5.2.6 Expedited Reporting Requirements for Arm X (Arms A and B) on protocol E2112

Investigational Agents: Entinostat/Placebo

Commercial Agents: Exemestane

*When an investigational agent is used in combination with a commercial agent, the combination is considered to be investigational and expedited reporting of adverse events follows the guidelines for investigational agents.*

Late Phase 2 and Phase 3 Studies

Expedited Reporting Requirements for Adverse Events that Occur on Studies under an IND/IDE within 30 Days of the Last Administration of the Investigational Agent/Intervention.

**NOTE:** Footnote 1 instructs how to report serious adverse events that occur more than 30 days after the last administration of investigational agent/intervention.

**FDA REPORTING REQUIREMENTS FOR SERIOUS ADVERSE EVENTS (21 CFR Part 312)**

**NOTE:** Investigators **MUST** immediately report to the sponsor (NCI) **ANY** Serious Adverse Events, whether or not they are considered related to the investigational agent(s)/intervention (21 CFR 312.64)

An adverse event is considered serious if it results in **ANY** of the following outcomes:

1. Death
2. A life-threatening adverse event
3. An adverse event that results in inpatient hospitalization or prolongation of existing hospitalization for  $\geq 24$  hours
4. A persistent or significant incapacity or substantial disruption of the ability to conduct normal life functions
5. A congenital anomaly/birth defect.
6. Important Medical Events (IME) that may not result in death, be life threatening, or require hospitalization may be considered serious when, based upon medical judgment, they may jeopardize the patient or subject and may require medical or surgical intervention to prevent one of the outcomes listed in this definition. (FDA, 21 CFR 312.32; ICH E2A and ICH E6).

**ALL SERIOUS** adverse events that meet the above criteria **MUST** be immediately reported to the NCI via CTEP-AERS within the timeframes detailed in the table below.

Hospitalization	Grade 1 Timeframes	Grade 2 Timeframes	Grade 3 Timeframes	Grade 4 & 5 Timeframes
Resulting in Hospitalization $\geq 24$ hrs	10 Calendar Days			24-Hour 5 Calendar Days
Not resulting in Hospitalization $\geq 24$ hrs	Not required	10 Calendar Days		

**NOTE:** Protocol-specific exceptions to expedited reporting of serious adverse events are found in the Specific Protocol Exceptions to Expedited Reporting (SPEER) portion of the CAEPR.

**Expedited AE reporting timelines are defined as:**

- “24-Hour; 5 Calendar Days” – The AE must initially be reported via CTEP-AERS within 24 hours of learning of the AE, followed by a complete expedited report within 5 calendar days of the initial 24-hour report.
- “10 Calendar Days” – A complete expedited report on the AE must be submitted within 10 calendar days of learning of the AE.

 Serious adverse events that occur more than 30 days after the last administration of investigational agent/intervention and have an attribution of possible, probable, or definite require reporting as follows:

**Expedited 24-hour notification followed by complete report within 5 calendar days for:**

- All Grade 4, and Grade 5 AEs

**Expedited 10 calendar day reports for:**

- Grade 2 adverse events resulting in hospitalization or prolongation of hospitalization
- Grade 3 adverse events

Effective Date: May 5, 2011

Rev. 10/15  
Rev. Add5

5.2.7

Additional instructions, requirements and exceptions for protocol  
E2112

**Additional Instructions:**

- For instructions on how to specifically report events that result in persistent or significant disability/incapacity, congenital anomaly, or birth defect events via CTEP-AERS, please contact the AEMD Help Desk at [[contact]](mailto:[contact]) or [contact]. This will need to be discussed on a case-by-case basis.
- **Reporting a death on study:** A death occurring while on study or within 30 days of the last dose of treatment requires both routine and expedited reporting, regardless of causality. Attribution to treatment or other cause must be provided.

**NOTE:** A death due to progressive disease should be reported as a Grade 5 “Disease progression” under the System Organ Class (SOC) “General disorder and administration site conditions”. Evidence that the death was a manifestation of underlying disease (e.g. radiological changes suggesting tumor growth or progression: clinical deterioration associated with a disease process) should be submitted.

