**Table 9.2: Operating Characteristics for OS Endpoint**

Repeated Analysis	Real time (months)	Information time	Failures under alternative hypothesis	Nominal significance (one-sided)	Upper boundary
1	24	0.24	101	0.00048	3.3020
2	30	0.36	149	0.00048	3.3020
3	36	0.49	203	0.00068	3.2036
4	42	0.64	261	0.00400	2.6518
5	48	0.76	313	0.00805	2.4065
6	54	0.87	355	0.01193	2.2593
Final	64	1.00	410	0.01872	2.0808

If PFS test is negative in the primary analysis, this study will also be monitored for early stopping in favor of the null hypothesis (i.e., futility) for the OS test using the Jennison-Turnbull repeated confidence interval (RCI) method. At each interim OS analysis, the RCI on the observed hazard ratio will be computed using the critical values from the above error spending rate function. If the RCI does not include the alternative hazard ratio of 1.33 (arms B/A), then the OS comparison would be stopped early for lack of benefit. The observed hazard ratio will be calculated using stratified Cox proportional-hazards model, stratified on randomization stratification factors, without any other covariates. If the PFS test is positive in the primary analysis, no interim futility analysis for OS will be conducted.

As mentioned in Section 9.2.1, if the first interim analysis of OS is positive, the interim OS data will be released to Syndax and the public and the study will be stopped early for efficacy. If the first interim analysis of OS does not cross the efficacy boundary, then at the time study accrual is completed, if (1) the primary PFS test is positive at the 0.001 level, and (2) the estimated PFS hazard ratio for Exemestane + Entinostat vs. Exemestane + Placebo is  $< 0.675$ , the interim OS data will also be confidentially released to Syndax. The DSMC will also be asked to allow use of interim OS data from the first 360 patients enrolled in an application to the FDA, with the understanding that the data not be made public unless required as part of the FDA review process.

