#### 9.3.2 Toxicity

Another secondary endpoint of the study is to evaluate toxicities. Toxicity will be evaluated on the first 360 patients for the PFS analysis and on all patients for the OS analysis. All patients who start protocol therapy (i.e., receive at least one dose of protocol treatment) will be included in toxicity analysis. For the 360 patients for the PFS analysis, assuming 9 patients (9/180=5%) will not start protocol therapy in each arm, with 171 evaluable patients per arm, there is 92% power to detect a difference in grades 3-4 toxicity rate of 24% vs. 10% between arms A and B, assuming an one-sided type I error rate of 2.5%, based on the Fisher's exact test. For each arm, with 171 patients, the binomial exact 95% confidence interval for toxicity rate would be no wider than 0.16.

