at diagnosis, prior adjuvant chemotherapy, prior hormonal therapy, et al. The assumption of proportionality in the Cox models will be assessed by investigating the weighted Schoenfeld residuals for each predictor. Patients with missing values for covariates will be excluded from modeling when the proportion of missingness is less than 5% and will be imputed appropriately if the proportion of missingness is  $\geq 5\%$ . ORR will be summarized along with the exact binomial 95% confidence interval and compared between the two arms using Fisher's exact tests.

TTD is defined as time from randomization to disease progression or death or worsening of symptoms, whichever occurs first. All primary analysis for TTD will be based on all cases receiving at least one dose of protocol treatment (i.e., all treated population). The distribution of TTD will be estimated using Kaplan-Meier method, and TTD comparisons between treatment arms will be tested primarily using log-rank test. Cox proportional-hazards models will be conducted to estimate the HR for treatment effect for TTD as a supportive analysis. Same factors included in the multivariable Cox model for PFS and baseline symptom level will be included as predictors for TTD.

Analyses pertaining to toxicity will be based on all treated cases. Adverse events will be graded using the National Cancer Institute (NCI) Common Terminology Criteria for Adverse Events (CTCAE). All treatment-emergent and baseline adverse events and hematological/biochemical toxicities based on laboratory measurements, as well as drug related AE's, will be summarized by treatment group and NCI CTCAE worst grade. The incidence of deaths and treatment-emergent serious adverse events (defined as number of patients experiencing the AE divided by all treated patients) will be summarized and compared between treatment arms using Fisher's exact test. Also, the incidence of adverse events leading to discontinuation of investigational product and/or withdrawal from the study will be summarized and listed.

In all analyses, P-values will be two-sided. A level of 0.2% will be considered statistically significant for stratified log rank test for the primary PFS analysis. For OS comparison, the significance level for stratified log rank test will be 4.8%. For all other tests, a level of 5% will be considered statistically significant.

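### Section 9.4 compares deaths and serious adverse events between arms as toxicity without setting progression deaths apart, so efficacy can dilute an excess of harm

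*Combined protocol and SAP*

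**What the plan says.** Section 5.2.7 governs the reporting of deaths. A death on study or within 30 days of the last dose "requires both routine and expedited reporting, regardless of causality", and "Attribution to treatment or other cause must be provided". For progression it adds: "A death due to progressive disease should be reported as a Grade 5" event, under the term Disease progression, with supporting evidence. Sections 5.2.2 and 5.2.6 list death as an outcome that makes an adverse event serious, so a progression death in this window is also an SAE.

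Section 9.4 sets out the toxicity analysis in treated patients. "The incidence of deaths and treatment-emergent serious adverse events" will be "summarized and compared between treatment arms using Fisher's exact test". The section gives no exclusion for progression, no split by cause and no time window for deaths. On the level it says: "For all other tests, a level of 5% will be considered statistically significant", apart from the primary PFS and OS tests. Drug-related events are tabulated by arm and worst grade, and events leading to discontinuation are summarised and listed. Section 9.4 specifies no between-arm test for either.

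On timing, Section 9.3.2 says: "Toxicity will be evaluated on the first 360 patients for the PFS analysis". It is evaluated again on all patients at the OS analysis.

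**The concern.** Progression death is an efficacy outcome. If entinostat delays progression, as the trial hypothesises, the placebo arm will collect more Disease progression SAEs. Those offset any excess of other SAEs on the entinostat arm. Even with equal rates, they add noise that has nothing to do with toxicity. Deaths and SAEs are the only safety quantity for which Section 9.4 names a between-arm test, and the first 360 patients are the cohort intended for an FDA submission if PFS is positive (Section 9.2).

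The missing time window has a second consequence. Read literally, the death comparison at the PFS analysis counts every death by arm in that cohort. That is a crude survival comparison filed under toxicity, at a time when the plan holds interim OS closely.

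**Working it through.** **1. The plan's own figure.** Section 9.3.2 gives 92% power for grades 3-4 toxicity of 24% vs 10%, with 171 patients per arm, using Fisher's exact test at one-sided 2.5%. Exact enumeration of both binomials gives 92.2%, so the figure reproduces.

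**2. Assumptions for the illustration.** The documents give no SAE rates and no rate of progression death near the last dose. I borrow 24% vs 10% as an excess of SAEs not due to progression. I assume progression-death rates p_B of 2%, 5% or 8% on the placebo arm, independent of other SAEs.

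**3. Ratio of progression deaths, entinostat to placebo.** I let progression deaths follow progressions. With exponential PFS, medians of 4.1 and 7.1 months and uniform accrual over T = 24 months (Section 9.2.1), the cumulative event proportion is 1 − (1 − e^(−λT))/(λT), with λ = ln 2/median.

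- Placebo: λT = 4.057, proportion 0.758.
- Entinostat: λT = 2.343, proportion 0.614.
- Check: 180 × (0.758 + 0.614) = 247, the planned number of PFS events.
- Ratio: 0.614/0.758 = 0.81.

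**4. Any-SAE proportions and power.** Entinostat arm: A = 1 − 0.76 × (1 − p_A). Placebo arm: B = 1 − 0.90 × (1 − p_B). For example, with p_B = 5% and p_A = 0.81 × 5% = 4.05%, A = 1 − 0.76 × 0.9595 = 27.1% and B = 1 − 0.90 × 0.95 = 14.5%. The difference shrinks from 14.0 to 12.6 points on a higher base rate.

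| p_B | B | A, ratio 0.81 | Power | A, equal rates | Power |
|---|---|---|---|---|---|
| 0 (no progression deaths) | 10.0% | 24.0% | 92% | 24.0% | 92% |
| 2% | 11.8% | 25.2% | 87% | 25.5% | 89% |
| 5% | 14.5% | 27.1% | 79% | 27.8% | 83% |
| 8% | 17.2% | 28.9% | 69% | 30.1% | 77% |

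**5. The death comparison without a window.** At month 24, with 180 patients per arm, a control median OS of 22 months and HR 0.75 (Section 9.2.2), the same formula gives 29.8% dead on placebo and 23.7% on entinostat. A two-sided 5% Fisher test then favours entinostat in about 22% of trials, while the first OS boundary in Table 9.2 (0.00048 one-sided) is crossed in about 3%. With no OS effect, the Fisher test rejects in about 3.8% of trials, both directions together. These figures show how differently the two comparisons can read. They are not error rates for the OS claim.

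**The case against.** Several points on the other side stand.

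- **The coding rule is not at fault.** Section 5.2.7 makes progression deaths separable: they have their own term, and attribution and evidence are required. The gap is in Section 9.4, which counts deaths whatever their code.
- **A reader might infer that harm is hidden.** The documents do not support that. Drug-related events are tabulated by arm and grade. Section 9.4 defines incidence by patients with the event, which permits a term-by-term reading. On that reading Disease progression is its own row and dilutes nothing else. Dilution arises only if SAEs or deaths are pooled.
- **A reader might infer that the planned 92% power is lost.** It is not. That figure is for grades 3-4, so a Grade 5 event does not enter it. The early stopping rule in Section 9.2.3 counts Grade 4 non-hematologic events.
- **A reader might use the PFS hazard ratio of 0.58 as the ratio of progression deaths.** That gives 86%, 73% and 58%. But a hazard ratio is not a ratio of cumulative proportions, and the plan's own PFS assumptions give 0.81 at month 24.
- **A reader might infer that the 5% death test inflates the OS type I error.** It cannot. OS is rejected only through the stratified log-rank boundary, and the trial-wise level stays at 0.001 + 0.024 = 0.025. The 22% in step 5 is detection of a true effect.
- **Access is largely covered.** Section 9.9 restricts interim outcome data to the statistician and the DSMC, and lets only pooled or blinded toxicity data become public. After accrual is complete, if the PFS test is positive with a hazard ratio below 0.675, "the interim OS data will also be confidentially released to Syndax" in any case. What remains is that neither section says which rule covers a by-arm death table produced as toxicity.
- **All-cause comparison is a defensible safety choice.** A drug-related death misattributed to progression would drop out of a restricted test. This is a reason to keep the all-cause tables beside it.

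**Conclusion.** The point holds as a cheap improvement to Section 9.4. A pooled between-arm test of SAEs or deaths mixes efficacy with harm, and the section neither separates progression deaths nor sets a window for deaths. In the illustration the loss of power is about 3 to 15 points at equal rates (92% to 89-77%) and 5 to 23 points at a ratio of 0.81 (92% to 87-69%). The size rests on assumed progression-death rates of 2-8%, on independence from other SAEs, and on borrowing 24% vs 10% from the grades 3-4 statement. The direction does not depend on the exact rates. No primary analysis, powered toxicity statement or stopping rule is affected.

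**What to change.** Edit Section 9.4 only, and leave the reporting rule in Section 5.2.7 as it is.

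1. Make the between-arm SAE test exclude the Disease progression term, and show the all-cause SAE table alongside.
2. Report deaths by cause (progression, treatment-related, other) on treatment or within 30 days of the last dose.
3. State that any all-cause death comparison in the toxicity analysis is descriptive and cannot support an OS claim, and that its by-arm results stay with the statistician and the DSMC until OS is released under Sections 9.2.3 and 9.9.

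The cost is a few sentences. Cause and supporting evidence are already collected. The downside is that attribution to progression is a site judgement, though a blinded one, and the all-cause tables are kept for that reason. The change should be made before unblinding, so that which deaths count as toxicity is not chosen after the fact.
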